### 5.4 Analysis of binary outcomes with a single outcome per participant

For the binary outcomes, the intervention effect will be estimated using odds ratios (OR) with 95%Cl adjusted for clustering using RE logistic regression to adjust for within-school clustering. The models will include the cluster-level proportion with the baseline outcome measure and stratification variables. The LRT will be used to obtain p-values. The results will be presented as shown in Table A6.

### 5.5 Analysis of outcomes with repeated measures per participant

For secondary outcomes relating to school and class absence during menstruation, period-days are defined from the diary data as the school-days of menstruation (reported menstrual flow) plus the day prior to menstruation. The outcome measures are binary (see Table 2). For these data, there are repeated measures per girl, and analyses will additionally adjust for within-girl clustering (in addition to school-level clustering). This model will be fitted using RE logistic regression with both a random intercept for school and for student respectively. The analysis will include an interaction term between period (yes/no) and intervention arm to estimate the intervention effect on odds of absence of period-days relative to non-period days. To allow for the sampling fraction for diary data of 25 girls per school, the diary data will be weighted by the inverse of the school-level sampling fraction variables. The LRT will be used to obtain p-values. If there are problems with convergence using the random effects

model, robust standard errors will be used with clustering at school level. The results will be presented as shown in Table A6.

### 5.6 Effect-modification and mediation

Pre-specified potential effect modifiers are given in Table 3. In addition, we will assess baseline SDQ score and baseline UNEB exam score as individual-level effect-modifiers for the two primary outcomes, respectively.

Effect-modification for each of these variables with trial arm will be assessed for primary and selected secondary outcomes by fitting an interaction term with each variable and trial arm in the model. The strength of evidence (p-values) for effect-modification will be assessed using LRT.

We will also explore hypothesised causal pathways through mediation analyses specified in advance as part of the process evaluation.

Effect modifier	School/individual level	Measure
1. District	School level	Binary (Kalungu, Wakiso)
2. School ownership	School level	Binary (government, private)
3. Baseline UNEB exam z-score	School level	Binary (<0, ≥0)
4. S2 size (pre-intervention)	School level	Binary (median as cutoff: <59, ≥59)
5. School type (% boarding	School level	Binary (<50% boarding, >50% boarding)
students)		
6. Age group (at endline)	Individual level	Binary (median as cutoff)
7. Student type (day vs	Individual level	Binary (day, boarding)
boarding)		
8. Socio-economic status	Individual level	Binary (median as cutoff)

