## 2 Study Design

### 2.1 Trial design

The study was a parallel-arm, cluster-randomised controlled trial with a mixed-methods process evaluation, and economic and policy analyses. Schools (clusters) were randomised 1:1 to immediate delivery of the MENISCUS intervention or optimised usual care (provision of government menstrual management readers and circular). Schools randomised to the optimised usual care arm were offered the intervention after the endline assessment (approximately 1 year after randomisation). In this SAP, the term "intervention" refers to immediate intervention, and "control" to optimised usual care (delayed intervention, delivered after endline).

Female students who joined the S2-S3 class cohort during the intervention delivery period were eligible to be recruited. This "open cohort" design accommodates the dynamic school population, as students may both join and leave the class cohort during the intervention period. In the pilot study, 82% of participants present at baseline were present at the endline survey 9 months later [6]. Primary and secondary outcomes for female students will be assessed among participants present at endline, adjusting for cluster-level mean baseline measures of the relevant outcome where available. Knowledge and attitudes among male students will be assessed through a closed cohort. Further details are described in section 3.4 below.

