### 2.3 Sample size

The sample size of 60 schools was based on an anticipated harmonic mean of 60 female participants per school at endline. This sample size provides 84% power to detect a standardised mean difference of 0.2 for continuous outcomes, assuming an intra-cluster correlation ( $\rho$ ) of 0.05 and type 1 error of 0.05. The effect size of 0.2 is that observed for the primary outcome of SDQ score for girls in the pilot [6] and is considered moderate for educational outcomes and hence of policy relevance. The harmonic mean was used to account for variation in school size. We have not adjusted the type 1 error because the two primary outcomes are independent, and an improvement in one without the other will be informative.

The subsample of 1500 girls selected to provide daily diary data on school/class attendance and their menstrual cycle over 40 school days at endline provides >98% power to detect a 20% relative reduction on period-days at endline, based on pilot data [6] and ~89% power to detect this difference by district or other equally sized subgroups. From our pilot, we expect >95% of girls to be menstruating at endline, and this is accounted for in the power calculations where relevant.

Revised power calculations were conducted in March 2022 and reported to the IDMEC in April 2022 (report 1), following indication that due to COVID-19 closures and other reasons the harmonic mean school size may be smaller than 60. This showed that a harmonic mean of 40 female students per school at endline provides 80% power to detect a standardised mean difference of 0.2 assuming an ICC of 0.05.

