### 5.2 Analysis of continuous outcomes

The intervention effect for each primary outcome (educational attainment and SDQ) and continuous secondary outcomes will be presented as the adjusted mean difference in the endline scores between arms with corresponding 95% confidence intervals (CI). The effects will be estimated using linear random-effects (RE) models using a random intercept for school to adjust for within-school clustering. The model will be adjusted for the cluster-level mean of the baseline outcome measure and stratification variables (district and high/low school-level UNEB score). Likelihood ratio tests (LRT) will be used to obtain p-values. The results will be presented as shown in Table A5.

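### Effect modification by individual-level factors is tested without allowing the factor's effect to vary between schools, so the test is anti-conservative by an amount that depends on that unknown variation

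*SAP*

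**What the plan says.** - **Design.** "Schools (clusters) were randomised 1:1" (SAP 2.1), with 60 schools, so 30 per arm.
- **Model.** Section 5.2 analyses the continuous outcomes, including both primary outcomes, with "linear random-effects (RE) models using a random intercept for school to adjust for within-school clustering". It adjusts for the cluster-level baseline mean and the two stratification factors. No random coefficient is mentioned.
- **Effect modification.** Section 5.6 proceeds "by fitting an interaction term with each variable and trial arm in the model" and uses a likelihood ratio test for the p-value, for primary and selected secondary outcomes. I read this as the section 5.2 model plus the interaction, since no other model is named.
- **Modifiers.** Table 3 lists five school-level and three individual-level factors (age group, day or boarding, socio-economic status). In addition, "we will assess baseline SDQ score and baseline UNEB exam score as individual-level effect-modifiers for the two primary outcomes, respectively". Section 5.6 treats both kinds of modifier alike.
- **Elsewhere.** Section 5.7 has GEE with robust standard errors, aimed at informative cluster size, and cluster-level analyses. Neither is tied to the section 5.6 tests. The model checks in section 6.3 cover quadrature and non-normality only.

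**The concern.** For an individual-level modifier, each school supplies its own estimate of the modifier's effect (its slope). The modifier-by-arm term compares the average slope in 30 schools with that in 30 others. A random intercept absorbs differences between schools in mean outcome, not in slope. If the gap between boarders and day students, or the relation of endline to baseline score, differs from school to school, those differences are replicated only at school level. The model nevertheless judges the interaction against girl-level residual variation alone.

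The section 5.6 test is therefore valid only if the slope is the same in every school, which the SAP neither states nor checks. Otherwise the p-values for these subgroup findings are too small on average, and chance differences between schools may be read as evidence that the intervention works differently in some girls.

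**Working it through.** **Inputs from the SAP (section 2.3, and 2.1 for allocation)**
- "The sample size of 60 schools was based on an anticipated harmonic mean of 60 female participants per school at endline"; a revised calculation uses 40.
- Intra-cluster correlation "of 0.05 and type 1 error of 0.05". With outcome SD 1, the between-school variance is 0.05 (intercept SD √0.05 = 0.224) and the within-school variance 0.95. I take the test as two-sided; the SAP does not say.

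**Assumptions, not in the SAP**
- s, the between-school SD of the modifier's effect, in outcome SDs.
- v, the within-school variance of the modifier: 0.25 for a 50/50 split, 1 for a standardised continuous score.

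**Step 1: reproduce the plan's power.** Effective n per arm = 30m / [1 + (m − 1) × 0.05].
- m = 60: 1800/3.95 = 455.7. Power for a difference of 0.2 is 85.5% (normal) or 84.3% (t, 58 df). The SAP says "This sample size provides 84% power to detect a standardised mean difference of 0.2 for continuous outcomes".
- m = 40: 1200/2.95 = 406.8. Power is 81.4% (normal) or 80.1% (t). The SAP says "a harmonic mean of 40 female students per school at endline provides 80% power".

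Both figures reproduce, so these inputs are the plan's own.

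**Step 2: variance of the interaction.** One school's estimated slope has sampling variance 0.95/(m·v) plus true variance s². The interaction is a difference of two means of 30 slopes:
- actual variance: (2/30) × [0.95/(m·v) + s²]
- variance used by the random-intercept model: about (2/30) × 0.95/(m·v)
- ratio: f = 1 + s²·m·v/0.95

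The rejection rate under no true modification is 2[1 − Φ(1.96/√f)].

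Example, m = 60, v = 0.25, s = 0.2: 0.95/15 = 0.0633 and s² = 0.04, so f = 0.1033/0.0633 = 1.63 and √f = 1.277. Then 1.96/1.277 = 1.53 and the rate is 12.5%. The standard error should be 0.083, and the model uses about 0.065.

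**Step 3: results at nominal 5%, for 40 / 60 girls per school.** Binary s and continuous s/2 give the same formula value, because v is four times larger. The simulation columns come from 500 runs per setting (Monte Carlo SE about 1 point at 5%), with 60 schools, no true modification, and adjustment for arm, two strata and a cluster-level covariate.

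| Modifier | s | Formula | Simulated, random intercept | Simulated, random slope added |
|---|---|---|---|---|
| Binary 50/50 | 0 | 5.0 / 5.0% | 4.8 / 5.6% | 4.0 / 5.4% |
| | 0.1 | 6.2 / 6.9% | 3.8 / 7.0% | 2.8 / 4.8% |
| | 0.2 | 10.0 / 12.5% | 10.2 / 13.0% | 4.6 / 6.0% |
| | 0.3 | 16.0 / 20.8% | 13.0 / 18.8% | 5.0 / 4.6% |
| Continuous, SD 1 | 0.05 | 6.2 / 6.9% | 6.0 / 6.2% | 5.4 / 4.2% |
| | 0.10 | 10.0 / 12.5% | 10.6 / 13.8% | 5.8 / 6.2% |
| | 0.15 | 16.0 / 20.8% | 17.8 / 23.2% | 7.6 / 6.2% |

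The simulation broadly agrees with the formula, with some rates at 40 girls running lower. Over all settings run, the random-slope test rejected in 2.8% to 7.6%, and a t-test on school-specific slopes in 2.6% to 6.6%. The robust-variance fallback was not simulated.

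**Step 4: a less even split.** If 20% in each school have the characteristic, v = 0.2 × 0.8 = 0.16. At s = 0.2 the formula then gives 8.2% / 9.8% instead of 10.0% / 12.5%.

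**The case against.** The mechanism is hard to dispute, but its size is open to challenge.

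- **No slope variation is given.** A reader might infer that these tests reject two to six times too often. The SAP does not support a fixed multiple. Inflation is nil at s = 0 and slight for a binary modifier at s = 0.1. Six-fold inflation would need s of about 0.40-0.50 for a binary modifier, roughly twice the implied intercept SD of 0.224, or 0.20-0.25 for a standardised continuous one. This objection stands.
- **The continuous case may not arise.** Section 5.6 does not say how the individual baseline scores are entered, and every modifier in Table 3 is binary. The continuous rows apply only if the scores are kept continuous. This stands.
- **A 50/50 split in every school is the worst binary case.** Step 4 shows the reduction. This stands.
- **Clustering is not ignored.** A reader might infer that the analysis disregards the unit of randomisation. It does not: the random intercept remains, and clustering is incompletely modelled for one term.
- **No decision depends on these tests.** Section 5.6 presents p-values as strength of evidence, without a threshold. That these results would redirect the programme is conjecture. But Table A7 shows the p-value as the only inferential result for each modifier listed, so it should be valid.
- **Robust and cluster-level analyses are already planned.** They are sensitivity analyses with no link to section 5.6, so they show that the remedy is feasible but do not supply it.

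**Conclusion.** The point holds, with its size left open. As specified, the tests for the five individual-level modifiers omit between-school variation in the modifier's effect and are anti-conservative whenever such variation exists. For 40 to 60 girls per school, a nominal 5% becomes about 6-7%, 10-12.5% or 16-21% at slope SDs of 0.1, 0.2 and 0.3 for an evenly split binary modifier. The same rates apply at 0.05, 0.10 and 0.15 for a standardised continuous one. These figures rest on assumed slope SDs, equal school sizes, ICC 0.05 and a continuous outcome. Inflation is smaller where the modifier varies little within schools, as boarding status may. I made no calculation for binary or count secondary outcomes.

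The point does not reach the primary arm comparisons. Nor does it reach the five school-level modifiers, for which the random intercept already carries the relevant variation.

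**What to change.** In section 5.6, for individual-level modifiers only, add a school-level random slope for the modifier to the interaction model. If that model does not converge, take the interaction's p-value and confidence interval from school-clustered robust standard errors with a t reference on about 58 df (60 schools less 2). Keep the random-intercept model for the school-level modifiers. It would help to state in the same place whether the individual baseline scores enter as continuous or cut.

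This takes a sentence or two of wording and one extra variance term. Section 5.5 already accepts school-clustered robust standard errors as a fallback for the diary data. The price is wider intervals and lower power for these interactions: in the worked example the standard error rises from about 0.065 to 0.083. The random slope may also occasionally fail to converge, which the fallback covers.

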### 2.2 Changes to the design and analyses

A detailed description of all protocol amendments is included on pages 2-3 of the trial protocol version 6.0. Additional modifications to the measures defined for each secondary outcome are described in section 4.3 and Annex 2.

The secondary outcome on prevalence of bacterial vaginosis (BV), vaginal yeast and urinary tract infections (UTIs) among symptomatic girls was revised to the prevalence of UTIs only among symptomatic girls. This change was approved by the TSC to remove the time burden on schools, participants, and data collection teams.

The study protocol version 5.0 states that data will be analysed using mixed models for repeated measures (MMRM). This has been revised to mixed models adjusting for cluster level mean at baseline as described in section 0, as data were collected at only two time points.

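### The individual-level effect-modification tests adjust only for the school-mean baseline, although girls' own baseline scores exist; they stay valid but give up precision by an amount the plan does not let one fix

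*SAP*

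**What the plan says.** SAP section 5.2 defines the linear model for both primary outcomes, with a random intercept for school: "The model will be adjusted for the cluster-level mean of the baseline outcome measure and stratification variables". Section 2.1 also names the cluster-level mean as the baseline adjustment. Section 2.2 records the change from a repeated-measures model: "This has been revised to mixed models adjusting for cluster level mean at baseline", on the ground that there were only two data collection points.

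Section 5.6 then tests effect-modification "by fitting an interaction term with each variable and trial arm in the model" and names no further covariate. Table 3 lists eight modifiers, of which three are individual-level: age group, day versus boarding, and SES. The same section adds that "we will assess baseline SDQ score and baseline UNEB exam score as individual-level effect-modifiers for the two primary outcomes", so each baseline participant's own score on both primary outcomes is in the dataset.

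The footnote to Table A7, the shell for these results, mentions adjustment for the baseline outcome measure but not whether this is the school mean or the girl's own score.

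**The concern.** The interaction of arm with an individual-level modifier asks whether the gap between, say, older and younger girls in the same school differs between arms. That gap is estimated mainly within schools, and its precision depends mainly on the residual variance between girls in the same school. A covariate that takes one value per school cannot reduce that variance. The girl's own baseline score can, and it has already been collected.

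At stake is precision in pre-specified tests on both primary outcomes. Intervals for the difference between subgroup effects are wider than the data require, and a real difference by age or SES is more likely to be missed. The reason in section 2.2 does not settle this, since two time points are enough to adjust for an individual baseline score.

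**Working it through.** **Inputs from SAP section 2.3.** The design is given as "The sample size of 60 schools was based on an anticipated harmonic mean of 60 female participants per school at endline", with ICC 0.05 and "type 1 error of 0.05" (taken as two-sided). The stated results are "This sample size provides 84% power to detect a standardised mean difference of 0.2 for continuous outcomes" and, after revision, "a harmonic mean of 40 female students per school at endline provides 80% power".

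**Inputs not in the plan (assumptions).**
- r, the within-school correlation of baseline with endline score given the modifier: 0.3 to 0.7. It may differ between SDQ and UNEB.
- p, the share of endline girls with a baseline score: 0.82, range 0.7 to 1.0. The 82% in section 2.1 is the share of pilot baseline girls still present at endline, so it is only a stand-in.
- Modifier split 50:50 within every school, with a subgroup contrast that does not itself vary between schools.
- Interaction of 0.2 SD. This is the plan's main-effect size; it gives none for interactions.

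**Step 1: reproduce the stated power.** Design effect = 1 + (m − 1) × 0.05; effective number per arm = 30m / design effect.
- m = 60: design effect 3.95, effective 455.7 per arm; power 85.5% (normal) or 84.3% (t, 58 df). Stated: 84%.
- m = 40: design effect 2.95, effective 406.8 per arm; power 81.4% or 80.1%. Stated: 80%.

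Both reproduce.

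**Step 2: interaction SE under the plan.** The within-school variance is 1 − 0.05 = 0.95 in units of the total variance. With m/2 girls in each subgroup, a school's contrast has variance 4 × 0.95/m. Averaging over 30 schools per arm and differencing the arms gives

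SE = √(16 × 0.95 / (60m)).

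- m = 40: √(15.2/2400) = 0.0796.
- m = 60: √(15.2/3600) = 0.0650.

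**Step 3: add the girl's own baseline.** The within-school residual variance is multiplied by 1 − p × r², so the information forgone without the term is p × r². At p = 0.82:

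| r | Information forgone | SE, m = 40 | Power, m = 40 | SE, m = 60 | Power, m = 60 |
|---|---|---|---|---|---|
| plan as written | – | 0.0796 | 71.0% | 0.0650 | 86.8% |
| 0.3 | 7% | 0.0766 | 74.3% | 0.0625 | 89.2% |
| 0.5 | 21% | 0.0710 | 80.5% | 0.0579 | 93.2% |
| 0.7 | 40% | 0.0616 | 90.1% | 0.0503 | 97.8% |

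At r = 0.5 the interval is about 11% narrower. Over p = 0.7 to 1.0 and r = 0.3 to 0.7, the information forgone runs from 6% (0.7 × 0.09) to 49% (1.0 × 0.49).

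**Step 4: check by simulation.** A within-school estimator (60 schools of 40 girls, p = 0.82, 600 replicates per value of r) gave mean model-based variance reductions of 7%, 21% and 40% at r = 0.3, 0.5 and 0.7. A separate random-intercept simulation at r = 0.5, with the deviation set to 0 for a random 18% of girls (600 runs per cell), gave power of 72.8% rising to 82.0% at m = 40 and 85.5% rising to 92.3% at m = 60. It showed no bias, and null rejection rates were 3.5% to 5.7%.

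**Step 5: main effect.** Adding the individual score on top of the school mean changes main-effect power by about 0.1 to 0.9 points (r 0.3 to 0.7, school-level correlation 0 to 0.8).

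**The case against.** The strongest reply is that nothing here is an error. The interaction tests as written are unbiased and hold their level, they are supporting analyses, the SAP claims no power for them, and section 6.2 puts effect sizes and intervals ahead of p-values. That stands, and it limits the point to an inexpensive improvement. Interval width still matters under that emphasis, so the point does not fall away.

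The open cohort is also a better reason for the school mean than the two time points, because girls who joined later have no baseline score. This is fair, but a deviation set to 0 for those girls keeps them all in the analysis.

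The power figures are favourable to the concern. An interaction as large as the whole target effect is generous: at 0.1 SD with 40 girls per school, the SEs above give about 24% against 29% (r = 0.5), underpowered either way. A median cut-off need not split each school evenly, and the gain shrinks if the subgroup contrast varies between schools. These limits also stand.

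A reader might infer that the tests lose a fixed share of information, such as a fifth. The SAP does not support that: the figure needs r near 0.5 and p near 0.8, and it states neither.

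**Conclusion.** The point holds as an efficiency loss in the individual-level modifier tests: age, SES, and day/boarding in schools with both types. The information forgone is p × r², about 7% to 40% for r from 0.3 to 0.7 at an assumed p of 0.82. Under the Step 2 and 3 assumptions, the power gain for a 0.2 SD interaction is 2 to 3 points at r = 0.3, about 6 to 9 points at r = 0.5 and 11 to 19 points at r = 0.7, over 60 and 40 girls per school.

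A reader might go further and infer that the subgroup tests are biased or have an inflated type 1 error, or that the primary analysis is underpowered for the same reason. Neither follows. The plan's tests are valid, and for the main effect the school mean already captures nearly all of the gain. The point also does not touch the tests of individual baseline SDQ or UNEB as modifiers of their own outcome, because the score is then already in the model.

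**What to change.** In section 5.6, for the individual-level modifiers of the two primary outcomes:

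- Keep the school-mean baseline and the stratification variables.
- Add the girl's own baseline score as a deviation from the mean of the school where she took the baseline. That wording matters for girls who switched schools, whom section 3.5 analyses in their endline school.
- Set the deviation to 0 for girls without a baseline score, so that no joiner is dropped.
- Use the same term in any closed-cohort version of these tests.
- State in the Table A7 footnote which rows carry the individual term, and that the other baseline term is the school mean.

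Fix this before unmasking; if it is added later, label it supplementary. The cost is a few lines of SAP text and one covariate already in the dataset. The downside is that these rows come from a model with one more term than the main-effect model, and the gain is smaller where many girls have no baseline score.
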